#### **HOW TO CONVERT HYDROCODONE TO PF-06412528:**

- 1. Determine the total daily dose of hydrocodone.
- 2. Calculate the conversion of the total daily dose of the current hydrocodone therapy into the equianalgesic dose of morphine using the appropriate ratio (based on an approximate equianalgesic ratio of 1:1).
- 3. Refer to the analgesic table below to find the equianalgesic dose of PF-06412528. In general, it is safest to give half of the estimated daily morphine demand as the initial dose and to manage inadequate analgesia by supplementation with rescue medication.
- 4. Administer the calculated dose in the most convenient dosing strength of PF-06412528, either as a single dose q24h or in 2 divided doses q12h. PF-06412528 should not be given more frequently than every 12 hours.

#### **CONVERTING FROM HYDROCODONE TO PF-06412528:**

Hydrocodone daily dose (mg) a	Equianalgesic morphine daily dose (mg)	Suggested equianalgesic dose of PF-06412528 administered q24h or in 2 divided doses q12h (mg)	Suggested starting dose of PF-06412528 at ≈50% reduction based on existing capsule strengths (mg) b
20	20	20	10 QD
30	30	30	15 QD
40	40	40	10 BID
60	60	60	15 BID
80	80	80	20 BID

<sup>a Calculate the total daily dose of hydrocodone. At lower doses of hydrocodone, it may be necessary to start with the lowest strength of PF-06412528.

There is a lack of systematic evidence bearing on these types of analgesic substitutions. Therefore, specific recommendations are not possible. Healthcare professionals are advised to refer to published relative potency data, keeping in mind that such ratios are only approximate.

b It is likely that rescue medication may be needed for breakthrough pain until the dose of PF-06412528 can be titrated to the effective daily dose, thus ensuring a smooth transition.

In general, it is safest to give half of the estimated daily morphine demand as the initial dose and to manage inadequate analgesia by supplementation with rescue medication.

#### **HYDROMORPHONE PRODUCTS:**

- Dilaudid® (hydromorphone hydrochloride) Tablets, 2 mg, 4 mg, 8 mg; Dilaudid Oral Liquid, (5 mg/5 mL).
- Generic equivalent and other immediate-release (IR) products.

#### **HOW TO CONVERT FROM HYDROMORPHONE TO PF-06412528:**

- 1. Determine the total daily dose of hydromorphone.
- 2. Calculate the conversion of the total daily dose of the current hydromorphone therapy into the equianalgesic dose of morphine, using the appropriate ratio (based on an approximate equianalgesic ratio of 1:4).
- 3. Refer to the analgesic table below to find the equianalgesic dose of PF-06412528. In general, it is safest to give half of the estimated daily morphine demand as the initial dose and to manage inadequate analgesia by supplementation with rescue medication.
- 4. Administer the calculated dose in the most convenient dosing strength of PF-06412528, either as a single dose q24h or in 2 divided doses q12h. PF-06412528 should not be given more frequently than every 12 hours.

#### **CONVERTING FROM HYDROMORPHONE TO PF-06412528:**

Hydromorphone daily dose (mg) a	Equianalgesic morphine dose (mg)	Suggested equianalgesic dose of PF-06412528 administered q24h or in 2 divided doses q12h (mg)	Suggested starting dose of PF-06412528 at ≈50% reduction based on existing capsule strengths (mg) b
6	24	20	10 QD
8	32	30	15 QD
12	48	50	10 BID
16	64	60	15 BID
20	80	80	20 BID
24	96	100	30 BID

a Calculate the total daily dose of hydromorphone. There is a lack of systematic evidence bearing on these types of analgesic substitutions. Therefore, specific recommendations are not possible. Healthcare professionals are advised to refer to published relative potency data, keeping in mind that such ratios are only approximate.

b It is likely that rescue medication may be needed for breakthrough pain until the dose of PF-06412528 can be titrated to the effective daily dose, thus ensuring a smooth transition.

In general, it is safest to give half of the estimated daily morphine demand as the initial dose and to manage inadequate analgesia by supplementation with rescue medication.

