# 5.3. Study Drug Supplies

#### 5.3.1. Dosage Form(s) and Packaging

PF-06412528 (morphine sulfate and naltrexone hydrochloride extended release capsules) is a Schedule II (CII) oral dosage form available in the following strengths: 20 mg/0.8 mg, 30 mg/1.2 mg, 50 mg/2 mg, 60 mg/2.4 mg, 80 mg/3.2 mg, and 100 mg/4 mg. For purposes of this study, both a 10 mg/0.4 mg capsule and a 15 mg/0.6 mg capsule will be developed to meet the therapeutic needs of younger (lower weight) children. All PF-06412528 study drug, including the newly developed 10 mg/0.4 mg and 15 mg/0.6 mg capsule strengths, will be supplied by the Sponsor.

PF-06412528 study drug will be packaged and provided for use according to the total daily dose requirements of a subject as listed below:

Morphine Sulfate Total Daily Dose	Dosing Schedule	Capsule (dosage form)	Conversion/ Titration Phase Bottle Fill count (capsules/bottle)	Maintenance Phase Bottle Fill count (capsules/bottle)
10 mg	10 mg QD	CCI	10	20
15 mg	15 mg QD		10	18
20 mg	10 mg BID		20	36
30 mg	15 mg BID		20	36
40 mg	20 mg BID		20	36
60 mg	30 mg BID		20	36
80 mg	2x20 mg BID		40	72
100 mg	50 mg BID		20	36
120 mg	60 mg BID		20	36
160 mg	80 mg BID		20	36
200 mg	100 mg BID		20	36

No other medications, including rescue medications, will be supplied by the Sponsor.

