#### **5.4.** Administration

PF-06412528 is to be administered with or without food, as per the investigator's Brochure. The bottle label will direct the subject to take either QD or BID depending on the total daily dose requirement for that subject (eg, children of low weight may be assessed to start with the 10 or 15 mg dose QD. Those labels will indicate QD dosing. Dosing strengths greater than 15 mg will indicate BID dosing). When given BID, one dose must be administered in the morning and the second dose is to be administered approximately 12 hours later. Morning doses should be encouraged to be administered daily between 6:00-10:00 AM throughout the study. As a general rule, the initial calculated daily dosage of PF-06412528 should be reduced by 50% and then titrated to achieve a stable dose. When converting to PF-06412528, the investigator should consider the potency, route of administration, and total daily dose of the discontinued opioid(s), the medical status of the subject, the subject's degree of opioid experience and tolerance, the type and severity of chronic pain, and the use of concomitant rescue medications to control the pain. Because

steady-state plasma concentrations are approximated within 24 to 36 hours, PF-06412528 dosage adjustments may be done as frequently as every 1 to 2 days. Study drug will be dispensed to the subject's caregiver only.

When PF-06412528 extended-release capsules are administered whole, the naltrexone remains intact and does not affect the analgesic potential of morphine. However, if the capsule is crushed, chewed or dissolved, the naltrexone component is released, competitively binds at the mu-opioid receptors, thus inhibits the effects of the opioid.

Therefore, PF-06412528 extended-release capsules are to be swallowed whole. The pellets in the capsules are not to be crushed, chewed, or dissolved prior to swallowing.

The co-ingestion of PF-06412528 with alcohol could result in an increase in morphine plasma levels and potentially fatal overdose of morphine. Subjects should not consume alcoholic beverages or use prescription or non-prescription products containing alcohol while on PF-06412528 therapy.

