#### **Appendix 2. Conversion Guide**

#### PF-06412528 CONVERSION GUIDE

This conversion guide summarizes published relative potency data to help healthcare professionals convert treatment regimens for subjects with moderate to severe chronic pain to an approximate daily equianalgesic dose of PF-06412528. The conversion ratios in this guide are for converting from other opioids to PF-06412528 only. Only oral and transdermal (not rectal) conversion information is provided. These conversion ratios are only approximate and are not to be used in the reverse.

The tables included in this booklet should be considered for guidance only, and the actual dose of any opioid product should be based on clinical judgment and adjusted on an individual basis.

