#### IMPORTANT INFORMATION ABOUT THIS GUIDE:

Due to incomplete cross-tolerance when converting from a non-morphine analysis to PF-06412528, the following equianalgesic conversion tables should be used with some degree of caution. For this reason, it is better to underestimate the subject's 24-hour oral morphine requirement and provide rescue medication rather than to overestimate and manage an adverse event.

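### Appendix 2, hydromorphone 24 mg/day: the 30 BID start is 60 to 62.5% of the converted dose, and the guide's own caution favours 20 BID

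*Protocol*

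**What the plan says.** Sections 3.2.1 and 6.2.1 (Visit 2) take the starting dose from the Conversion Guide in Appendix 2. For hydromorphone, the guide converts to morphine "based on an approximate equianalgesic ratio of 1:4" and then advises: "In general, it is safest to give half of the estimated daily morphine demand as the initial dose". The last column of the table is headed "Suggested starting dose of PF-06412528 at ≈50% reduction based on existing capsule strengths (mg". The row for 24 mg/day reads 96 mg morphine, 100 mg equianalgesic study drug, start 30 BID.

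The introductory caution on incomplete cross-tolerance, which concerns conversion from non-morphine analgesics, says that "it is better to underestimate the subject's 24-hour oral morphine requirement and provide rescue medication rather than to overestimate". The guide also states: "The tables included in this booklet should be considered for guidance only".

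Section 5.3.1 fixes the regimens that can be supplied: "PF-06412528 study drug will be packaged and provided for use according to the total daily dose requirements of a subject as listed below". The listed daily totals are 10, 15, 20, 30, 40, 60, 80, 100, 120, 160 and 200 mg. Section 5.4 gives its own general rule, that the initially calculated daily dose of study drug be cut by half and then titrated. On frequency it says: "Dosing strengths greater than 15 mg will indicate BID dosing".

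**The concern.** A 60 mg/day start cuts the 96 mg equivalent by 37.5%, under a heading of about 50%. Two rounding steps lead there, and both go up: 96 to 100 mg, then half of 100 (50 mg) to 60 mg. A lower listed dose, 40 mg/day, is available and is closer to half of the 96 mg.

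The guide asks for caution in the other direction when the prior opioid is not morphine. The subjects are children aged 7 to 17 moving to an extended-release opioid, so a start that errs high is the less safe error. What is at stake is the first dose for a child converted from this one hydromorphone dose. Nothing in the safety or pharmacokinetic analysis depends on it.

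**Working it through.** **Inputs.** The 1:4 ratio and the table rows come from Appendix 2, hydromorphone. The listed daily totals come from Section 5.3.1.

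**Reproducing the plan's figure.** 24 × 4 = 96 mg, as printed. The printed start is 2 × 30 = 60 mg/day.

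**Base 1: the morphine equivalent (second column).**
- Half of 96 is 48 mg. The listed neighbours are 40 and 60 mg/day.
- Distances: 48 − 40 = 8 mg; 60 − 48 = 12 mg. The nearest dose is 40 mg/day (20 BID).
- Printed start: 60/96 = 62.5%, which is 12.5 points from 50%.
- Alternative: 40/96 = 41.7%, which is 8.3 points from 50%.

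**Base 2: the rounded study-drug dose (third column).**
- Half of 100 is 50 mg. Distances: 50 − 40 = 10 mg; 60 − 50 = 10 mg. This is a tie.
- Printed start: 60/100 = 60%. Alternative: 40/100 = 40%.

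A start of 50 mg/day is not available. Section 5.3.1 lists no such total, and Section 5.4 assigns strengths above 15 mg to BID dosing, which rules out one 50 mg capsule daily.

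**The row within its own table.**

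| Hydromorphone (mg/day) | Morphine equivalent (mg) | Rounded dose (mg) | Printed start (mg/day) | Start, % of equivalent | Start, % of rounded dose |
|---|---|---|---|---|---|
| 6 | 24 | 20 | 10 | 41.7 | 50.0 |
| 8 | 32 | 30 | 15 | 46.9 | 50.0 |
| 12 | 48 | 50 | 20 | 41.7 | 40.0 |
| 16 | 64 | 60 | 30 | 46.9 | 50.0 |
| 20 | 80 | 80 | 40 | 50.0 | 50.0 |
| 24 | 96 | 100 | 60 | 62.5 | 60.0 |

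The 12 mg row poses the same choice at half scale: 48 rounds to 50, half is 25, and the listed neighbours are 20 and 30. It goes down, to 10 BID. The 24 mg row goes up. So 24/12 = 2 in hydromorphone becomes 60/20 = 3 in the start. From 20 to 24 mg, the equivalent rises by 96/80 = 1.20 and the start by 60/40 = 1.50.

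**The row within the whole guide (37 rows, seven tables).** Measured on the morphine equivalent, 22 rows start at exactly 50%, 9 below and 6 above, with a range of 41.7 to 62.5%. The 24 mg row is the maximum. On that base 33 rows are at the single nearest listed dose, 3 are ties (fentanyl 75 mcg/h, methadone 60 mg, morphine 100 mg), and the hydromorphone 24 mg row alone is at neither. Measured on the rounded dose, every row is nearest or tied, and the hydromorphone 24 mg row shares its 60% with morphine 100 mg.

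The three rows at 90 mg morphine equivalent (methadone 30 mg, morphine 90 mg, oxycodone 60 mg) all start at 40 mg/day.

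**The case against.** The strongest reply is that the table halves the third column. Section 5.4 speaks of halving the calculated dose of study drug, and the printed figures fit that reading. The second and third columns differ in six rows (hydromorphone 6, 8, 12, 16 and 24 mg; oxycodone 30 mg). In four of them the start is exactly half of the third column; in none is it exactly half of the second. On that base 40 and 60 mg/day are tied. The prose beside the hydromorphone table does say to halve the estimated morphine demand, so the base is ambiguous. This part of the reply stands. A reader might infer that the cell is a calculation error, or the one faulty row of 37. The documents support neither without choosing the base, and they state no nearest-dose rule.

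Second, morphine 100 mg has the same third column and the same 30 BID start, and its step from the 90 mg row is steeper (equivalent up 11%, start up 50%). That is also true, and it shows that the jump partly reflects the gap between 40 and 60 mg/day. But 100 mg is an exact tie on both bases, and the cross-tolerance caution concerns non-morphine drugs. Methadone 60 mg also breaks a tie upward. It too is an exact tie on both bases, and at 55.6% it is nearer to half.

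Third, the tables are guidance, a footnote calls the ratios approximate, and Section 5.4 leaves the dose to the investigator's judgment. A reader might infer an overdose risk, but none is shown: 60 mg/day is still 36 mg below the 96 mg estimate, in children who must already be taking opioids. These points limit the size of the concern. They do not explain why this cell goes up where its companion row goes down.

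**Conclusion.** The point holds as an inconsistency in one cell, on the less cautious side. The printed start is 12 mg/day above half of the morphine equivalent, or 10 mg/day above half of the rounded dose. Against the morphine equivalent 20 BID is nearer; against the rounded dose it is tied. The caution for non-morphine opioids and the 12 mg row then settle the choice in favour of 20 BID on either base.

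This rests on the guide's 1:4 ratio and on the Section 5.3.1 list being the full set of regimens. The documents do not say how many subjects would enter on hydromorphone 24 mg/day, so the number affected is unknown. Severity is minor: a dosing-safety improvement with no effect on sample size, endpoints or analysis.

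**What to change.** In the hydromorphone table of Appendix 2, change the starting dose for 24 mg/day from 30 BID to 20 BID. The start becomes 41.7% of 96 mg, the same as the 6 and 12 mg rows, and 40 mg/day as in the three 90 mg rows. Doubling hydromorphone from 12 to 24 mg then doubles the start (20 to 40 mg/day). The morphine 100 mg and methadone 60 mg rows can stay.

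The cost is one table cell and a note to sites. The downside is a start 20 mg/day lower, the same as in the 20 mg row, with possible early under-treatment or withdrawal; morphine 100 mg would also keep its 60 mg/day start. The protocol already covers the risk. Visit 2 allows rescue medication, including IR morphine, and Section 5.4 states that "PF-06412528 dosage adjustments may be done as frequently as every 1 to 2 days".

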#### **METHADONE PRODUCTS:**

- Dolophine® Hydrochloride (methadone hydrochloride tablets, USP) 5 mg, 10 mg.
- Methadose® Dispersible Tablets, 40 mg (methadone hydrochloride tablets for oral suspension USP) and Methadone Hydrochloride Tablets USP, 40 mg (dispersible, orange flavored) (methadone hydrochloride tablets for oral suspension USP); Methadose Oral Concentrate (methadone hydrochloride oral concentrate USP) 10 mg/mL; Methadose Sugar-Free Oral Concentrate (methadone hydrochloride oral concentrate USP) dye-free, sugar-free, unflavored, 10 mg/mL.
- Generic equivalent and other immediate-release (IR) products.

#### **HOW TO CONVERT METHADONE TO PF-06412528:**

- 1. Determine the total daily dose of methadone.
- 2. Calculate the conversion of the total daily dose of the current methadone therapy into the equianalgesic dose of morphine, using the appropriate ratio (based on an approximate equianalgesic ratio of 1:3-15). 9,10
- 3. Refer to the analgesic table below to find the equianalgesic dose of PF-06412528. In general, it is safest to give half of the estimated daily morphine demand as the initial dose and to manage inadequate analgesia by supplementation with rescue medication.
- 4. Administer the calculated dose in the most convenient dosing strength of PF-06412528, either as a single dose q24h or in 2 divided doses q12h. PF-06412528 should not be given more frequently than every 12 hours.

### CONVERTING FROM METHADONE TO PF-06412528:

Methadone daily dose (mg) a	Equianalgesic morphine dose (mg)	Suggested equianalgesic dose of PF-06412528 administered q24h or in 2 divided doses q12h (mg)	Suggested starting dose of PF-06412528 at ≈50% reduction based on existing capsule strengths (mg) b
20	60	60	15 BID
30	90	90	20 BID
40	120	120	30 BID
50	150	150	2X20 BID
60	180	180	50 BID
80	240	240	60 BID
100	300	300	80 BID

a. Calculate the total daily dose of methadone.

There is a lack of systematic evidence bearing on these types of analgesic substitutions. Therefore, specific recommendations are not possible. Healthcare professionals are advised to refer to published relative potency data, keeping in mind that such ratios are only approximate.

b. It is likely that rescue medication may be needed for breakthrough pain until the dose of PF-06412528 can be titrated to the effective daily dose, thus ensuring a smooth transition.

Data on the equianalgesic dose of methadone compared with morphine are inconclusive. Conversion ratios in many commonly used equianalgesic dosing tables do not apply in the setting of repeated methadone dosing. Although with single-dose administration, the onset and duration of analgesic action as well as the analgesic potency of methadone and morphine are similar, methadone's potency increases over time with repeated dosing.

In general, it is safest to give half of the estimated daily morphine demand as the initial dose and to manage inadequate analgesia by supplementation with rescue medication.

#### **OTHER MORPHINE PRODUCTS:**

- Avinza® (morphine sulfate extended-release capsules) 30 mg, 45 mg, 60 mg, 75 mg, 90 mg, 120 mg.
- Kadian® (morphine sulfate extended-release) Capsules, 10 mg, 20 mg, 30 mg, 50 mg, 60 mg, 80 mg, 100 mg, 200 mg.
- MS Contin® (morphine sulfate controlled-release) Tablets, 15 mg, 30 mg, 60 mg, 100 mg, 200 mg.
- Oramorph® SR (morphine sulfate) sustained release tablets, 15 mg, 30 mg, 60 mg, 100 mg.
- Generic equivalent and other immediate-release (IR) products.

#### HOW TO CONVERT FROM OTHER MORPHINE PRODUCTS TO PF-06412528:

- 1. Determine the total daily dose of the current opioid therapy being used.
- 2. Calculate the conversion of the total oral daily dose of the current morphine therapy into the equianalgesic dose of morphine, using the appropriate ratio (1:1).
- 3. Refer to the specific analgesic table below to find an equianalgesic dose of PF-06412528.
- 4. Administer the calculated dose in the most convenient dosing strength of PF-06412528, either as a single dose q24h or in 2 divided doses q12h. PF-06412528 should not be given more frequently than every 12 hours.

#### CONVERTING FROM OTHER MORPHINE PRODUCTS TO PF-06412528:

Morphine daily oral dose (mg) a	Equianalgesic morphine oral dose (mg)	Suggested equianalgesic dose of PF-06412528 administered q24h or in 2 divided doses q12h (mg)	Suggested starting dose of PF-06412528 at ≈50% reduction based on existing capsule strengths (mg) b
30	30	30	15 QD
60	60	60	15 BID
90	90	90	20 BID
100	100	100	30 BID
200	200	200	50 BID

a Calculate the total daily morphine dose. This amount can be given as PF-06412528 in a single daily q24h dose or in 2 divided doses q12h.

To convert from parenteral morphine, a dose of oral morphine 3 times the daily parenteral morphine requirement may be sufficient in chronic use settings.

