#### 6.2.1. Conversion/Titration Phase

### Pre-Dose Visit 2 (Day 1)

During this visit (Study Day 1) the following procedures will be followed before the administration of study medication:

- Review any results from laboratory samples (hematology, chemistry, urinalysis, pregnancy tests) that may exclude a subject from participating.
- **Pregnancy Test:** Take a urine sample from all females of childbearing potential.
- Vital Signs.

- SIB Assessment: C-SSRS (Section 7.4.1):
  - Children's Since Last Visit (Ages 7-11) (Version 6/23/10)-(Appendix 5).
  - Since Last Visit (Ages 12-17) (Version 1/14/09)-(Appendix 6).
- COWS assessment.
- **Opioid Therapy Review:** Review standard of care opioid therapy and document name of all opioids, dose, and dosing frequency.
- Concomitant medications: Review and document concomitant medication use (name, dose, and frequency).
- Adverse Event Assessment with focus on serious: Only pre-dose serious adverse events will be documented.
- Pain Intensity: In-clinic assessment.
- Discontinue previous standard of care opioid therapy as part of dose conversion.
- Prescribe Rescue Medication (if needed): Prescribe rescue medication (acetaminophen and/or NSAID's) to be used during conversion and titration. IR morphine may also be prescribed for rescue, with the intent to limit its use until a stable dose is achieved.
- **Dispense Study Drug:** Dispense appropriate dose of PF-06412528 based on the **Conversion Guide** (as described in Appendix 2).
- Caregiver(s) Training and Subject Instruction: Train the caregiver(s) and instruct the subject on study medication administration and recording of drug accountability, including recording the date/clock time of study drug administration, rescue medication use, analgesia assessments and adverse events between visits in the diary.
- Schedule the Visit 3a (Day 7±2 days) visit.

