#### **HOW TO CONVERT OXYCODONE TO PF-06412528:**

- 1. Determine the total daily dose of oxycodone.
- 2. Calculate the conversion of the total daily dose of the current oxycodone therapy into the equianalgesic dose of morphine, using the appropriate ratio (based on an approximate equianalgesic ratio of 1:1.5).

b Consider giving the subject rescue medication to make up the difference (if the starting dose is less than an equianalgesic dose) until the dose of PF-06412528 is titrated to the effective daily dose.

- 3. Refer to the analgesic table below to find the equianalgesic dose of PF-06412528. In general, it is safest to give half of the estimated daily morphine demand as the initial dose and to manage inadequate analgesia by supplementation with rescue medication.
- 4. Administer the calculated dose in the most convenient dosing strength of PF-06412528, either as a single dose q24h or in 2 divided doses q12h. PF-06412528 should not be given more frequently than every 12 hours.

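### Appendix 2's morphine section can be read as starting at 100% of the prior daily morphine dose, while its own starting-dose column and Protocol Section 5.4 call for about 50%

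*Protocol*

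**What the plan says.** Protocol Section 3.2.1 has the first dose determined from the Conversion Guide in Appendix 2. Section 6.2.1 repeats this for Visit 2: "Dispense appropriate dose of PF-06412528 based on the" guide.

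The guide's section on other morphine products contains the following:

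- Step 2 converts oral morphine at 1:1. Step 3 sends the investigator to the table for an equianalgesic dose. Step 4 reads "Administer the calculated dose in the most convenient dosing strength of PF-06412528", either once every 24 hours or divided every 12 hours. No step mentions a reduction.
- Footnote a, attached to the prior-dose column, says to total the daily morphine dose and adds "This amount can be given as PF-06412528 in a single daily q24h dose or in 2 divided doses q12h".
- The last column is headed "Suggested starting dose of PF-06412528 at ≈50% reduction based on existing capsule strengths (mg)". Footnote b to that column (displaced into the oxycodone steps in the extracted text) says "Consider giving the subject rescue medication to make up the difference (if the starting dose is less than an equianalgesic dose)" until titration reaches the effective dose.
- A closing note converts parenteral morphine to oral at three times the parenteral requirement, described as possibly sufficient in chronic use.

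Protocol Section 5.4 states, as a general rule and with no exemption for morphine, that "the initial calculated daily dosage of PF-06412528 should be reduced by 50% and then titrated to achieve a stable dose". In Section 5.3.1 only the 10 mg and 15 mg totals are once-daily regimens. Section 5.4 has strengths above 15 mg labelled for twice-daily use.

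**The concern.** The morphine steps, followed in order, never reach the starting-dose column. They go from a 1:1 conversion to an equianalgesic dose to giving the calculated dose, and footnote a then says the total daily amount can be given as study drug. An investigator could take this as a start at the full prior dose, which Section 5.4 does not intend.

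Two features belong to the morphine section alone. The other six drug sections each tell the reader that "it is safest to give half of the estimated daily morphine demand as the initial dose", once in step 3 and once with the table, and the morphine section does not say it at all. The footnote a wording also occurs nowhere else in the guide.

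This is the child's first dose of study drug. Two sites, both believing they follow the guide, could start similar children about two-fold apart. Symptoms of opioid toxicity or withdrawal are part of the primary safety endpoint (Section 2.2.1), and adverse events are summarised separately for the Conversion/Titration Phase (Section 9.4.1), where such differences would fall.

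**Working it through.** **Inputs.** Prior dose, equianalgesic dose and starting dose come from the morphine table in Appendix 2. Available regimens come from Section 5.3.1. The entry minimum of 20 mg/day morphine equivalent comes from Section 4.1, criterion 3.

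**Formulas.** Starting total per day = capsule dose × 1 for QD, × 2 for BID. Starting fraction = starting total / prior daily dose. Ratio of readings = full-dose reading / starting total. At 1:1, the full-dose reading equals the prior daily dose.

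| Prior oral morphine = full-dose reading (mg/day) | Starting column | Starting total (mg/day) | Starting fraction | Ratio of readings |
|---|---|---|---|---|
| 30 | 15 QD | 15 | 15/30 = 50% | 30/15 = 2.00 |
| 60 | 15 BID | 30 | 30/60 = 50% | 60/30 = 2.00 |
| 90 | 20 BID | 40 | 40/90 = 44.4% | 90/40 = 2.25 |
| 100 | 30 BID | 60 | 60/100 = 60% | 100/60 = 1.67 |
| 200 | 50 BID | 100 | 100/200 = 50% | 200/100 = 2.00 |

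**The plan's own figure reproduces.** The mean starting fraction is (50 + 50 + 44.4 + 60 + 50)/5 = 50.9%, which agrees with the column's stated reduction of about 50%.

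**A dose with no row.** At the entry minimum of 20 mg/day, the steps give 20 mg/day. Section 5.4 gives 0.5 × 20 = 10 mg/day, which is 10 mg QD. The ratio is 20/10 = 2.00.

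**Would supplies block the full-dose reading?** Mostly not. Section 5.3.1 lists twice-daily regimens for totals of 30, 60, 100 and 200 mg. It lists none for 90 mg, so in that row only the reduced start can be supplied as listed.

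**Footnote a's single daily dose.** The full amounts are 30 to 200 mg. None is a once-daily regimen in Section 5.3.1, so that option does not fit the protocol in any row.

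**Parenteral morphine (illustrative dose).** For 20 mg/day parenteral, the calculated oral dose is 3 × 20 = 60 mg/day. The steps would give 60 mg/day; half is 30 mg/day (15 mg BID). Here the calculated dose is an estimate across routes, so the full-dose reading does not simply continue the child's present oral dose. Amendment 2 opened the trial to post-surgical children.

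**Count of the halving sentence.** Fentanyl, hydrocodone, hydromorphone, methadone, oxycodone and oxymorphone: 6 sections × 2 = 12. Morphine: 0.

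**The case against.** The strongest reply is that a careful reader would not be misled. The table has two separately labelled columns, only one of them headed as a starting dose, and Visit 2 is the start. Section 5.4 gives the same rule. Footnote b describes a reduced start followed by titration, and the 10 and 15 mg once-daily starts lie below the 20 mg/day entry minimum. Footnote a sits on the prior-dose column and may be only a remark on dosing frequency. Step 4 has the same wording in all seven drug sections. The guide's introduction says its tables are guidance subject to clinical judgment, so some variation between sites is expected by design. Its caution about incomplete cross-tolerance concerns non-morphine opioids, which may be why the halving sentence was left out for morphine.

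Most of this stands, and it rules out calling the text two equal and opposed rules. It does not remove the ambiguity. Step 4 is shared, but only in the morphine section is it not preceded by advice to halve. Footnote b is conditional and leaves open a start at the equianalgesic dose. If the omission was deliberate, neither Section 5.4 nor the starting-dose column says so. If footnote a concerns frequency, its single daily dose still does not fit Section 5.3.1.

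A reader might also infer that children would be overdosed. For oral morphine the documents do not support that: 1:1 conversion keeps the current total daily dose, and the 1.67 to 2.25 ratios compare with a deliberately reduced start. Nor need this be the child's first extended-release opioid, since the listed sources include "morphine sulfate extended-release capsules) 30 mg, 45 mg, 60 mg, 75 mg, 90 mg, 120 mg". Prior opioid experience, rescue medication and dose adjustment every 1 to 2 days limit harm under either reading.

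**Conclusion.** The point holds as an ambiguity in a first-dose instruction for children. Followed literally, the morphine steps and footnote a give 100% of the prior daily dose. The starting-dose column gives 44% to 60%, and Section 5.4 gives 50%. The full-dose reading is therefore 1.67 to 2.25 times the intended start, and 2.00 times at the 20 mg/day entry minimum. These ratios assume oral morphine at 1:1. For parenteral sources the calculated dose also rests on the three-fold estimate.

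The protocol as a whole favours about 50%. A reader might infer an outright contradiction, or a measurable distortion of adverse event rates. The first goes too far for the reasons above. The second cannot be shown, because the documents do not say how many children will enter on morphine or how sites will read the section. The safety analysis is descriptive, and no sample size, power or error rate depends on this. The text should still be corrected, because it governs the first dose and the correction is small.

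**What to change.** In the morphine section of Appendix 2:

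1. Have steps 3 and 4 direct the investigator to the starting-dose column for the Visit 2 dose.
2. For doses without a row, and for oral equivalents estimated from parenteral morphine, specify 50% of the calculated oral dose, rounded to a regimen listed in Section 5.3.1 (for example, 20 mg/day to 10 mg QD).
3. Reword footnote a so that the total daily dose is the equianalgesic reference for titration, with QD or BID dosing as in Section 5.3.1.

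If the sponsor intends a 1:1 switch for oral morphine, state that exemption and change the starting-dose column and Section 5.4 to match.

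The cost is a few sentences in one drug section and a note to sites (for the exemption, also the column and Section 5.4). No procedures, supplies or patients are added.
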